NP and OP Swabs		X		X		X	X	X	X		Based on Part 1 data, NP and OP swab collection may be adapted to remove one method or timepoints throughout the life of the study; this will be communicated via Protocol Clarification Letters.
Serum and Plasma for Exploratory Research		X				X	X		X		Research samples will be stored for testing as described in Sections 4.2.5 and 8.8.
Serum for Antibody Exploratory Research		X				X	X		X		

Study Period:	Screening	Intervention					Follow-Up				Notes
Visit Number/Title:	1	2	3	4	5	6	7	8	9	10	
Scheduled Day (and Window):	Screening ( $\leq 24$ hours before rand.) a	Day 1 b	Day 2	Day 3	Day 4	EOT	Day 10 ( $\pm 1$ day)	Day 15 (+3 days)	Day 29 (+3 days)	LFU Month 7 ( $\pm 1$ Month) c	
Assessment of COVID-19 Signs, Symptoms, Functional Status		X	X	X	X	X	X	X	X		Assess signs and symptoms daily while hospitalized and only at study visits after discharge. Functional status only assessed at Day 1, Day 3, EOT, Days 10, 15, and 29. Assessment will not be done at virtual visits.
Assessment of Level of Consciousness (AVPU)		X				X					
Respiratory/ Oxygenation Status		X	X	X	X	X	X	X	X	X e	SpO 2 measured daily while hospitalized via pulse oximetry. If applicable: FiO 2 , PaO 2 , and supplemental oxygen use. SpO 2 will not be done at virtual visits.
Hospitalization Status		X	X	X	X	X	X	X	X	X	Discharge readiness will be assessed daily while hospitalized.
Survival Status									X	X	
Safety Procedures											
Full Physical Examination	X										Including height and weight
Directed Physical Exam		X		X		X	X	X	X		
Vital Signs	X	X	X	X	X	X	X	X	X		Heart rate, blood pressure, respiratory rate, temperature. Assess vitals daily while hospitalized and only on study visits after discharge.

Study Period:	Screening	Intervention					Follow-Up				Notes
		2	3	4	5	6	7	8	9	10	
Scheduled Day (and Window):	Screening ( $\leq 24$ hours before rand.) a	Day 1 b	Day 2	Day 3	Day 4	EOT	Day 10 ( $\pm 1$ day)	Day 15 (+3 days)	Day 29 (+3 days)	LFU Month 7 ( $\pm 1$ Month) c	
Blood Collection for Local Laboratory Evaluation	X d										Local laboratory collection required unless chemistry/hematology results within 72h prior to randomization are available.
Blood Collection for Central Laboratory Evaluation		X		X		X	X	X	X		Hematology and Chemistry at all indicated time points. Inflammatory biomarkers at Day 1 and EOT only.

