b Assessments required for COVID-19 severity categorization (Appendix 9) for IRT (vital signs, COVID-19 signs/symptoms assessment, respiratory measures, oxygen therapy, ongoing medical history) must be completed and documented on Day 1 prior to calling IRT in order to randomize. All other Day 1 assessments must be completed on Day 1 prior to first dose of study intervention.

c LFU (Month 7) visit is 7 months from the last dose of study intervention.

d The following local laboratory results must be available for all participants from within 72 hours prior to randomization to support determination of eligibility: serum creatinine, platelets, and absolute neutrophil count (segmented neutrophils and bands). In participants with reported history of HBV or HCV, ALT and AST must be available from within 72 hours prior to randomization to support determination of eligibility. In WOCBP, a negative local serum pregnancy test is required within 24 hours of the first dose of study drug per inclusion criteria. All other inclusion/exclusion criteria determination (eg, HIV status, pancreatitis, etc.) can be based on participant-reported medical history, available medical records, and the most recently available laboratory results for the participant (eg, HIV RNA viral load or CD4 count).

e Confirm no change in eligibility based on inclusion/exclusion criteria and/or disease severity.

f If participant is discharged prior to study intervention completion, study intervention and the Study Medication Diary will be dispensed to the participant according to the pharmacy manual.

g Respiratory/Oxygenation Status collection at the LFU visit will be limited. As LFU will be a virtual visit, SpO2 will not be measured. Use of supplemental oxygen will be collected.

h AEs, SAEs, and other reportable safety events (eg, pregnancy) will be monitored according to Section 8.4.

i A subset of ~100 participants will take part in the PBMC Cohort at selected sites.

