#### **6.3.2 Stratification**

Intervention randomization will be stratified according to the following factors:

1. Time from symptom onset prior to the day of randomization ( $\leq 5$  days,  $>5$  days)
2. Age ( $\leq 60$  years,  $>60$  years)
3. Remdesivir use for treatment of the index diagnosis of COVID-19 prior to or at the time of randomization (yes, no)

Based on the viral kinetics of SARS-CoV-2 and the mechanism of action of MK-4482, treatment with antiviral therapy is likely to have a greater benefit with early treatment ( $\leq 5$  days) rather than late treatment ( $>5$  days). Older age is also associated with more severe outcomes, and the WHO notes that people older than 60 years are at higher risk for severe illness due to COVID-19. Finally, remdesivir has been demonstrated to shorten the time to recovery in hospitalized patients with COVID-19 and may be used concurrently in this study. The selection of these criteria as stratification factors will help ensure that the treatment groups will be well balanced within each stratum and the study results will not be confounded by factors suspected to have a potential impact on a participant's response to study intervention.

Of note, enrollment of participants with severe COVID-19 (Appendix 9) will be limited to 50% of the total planned sample size in both Parts 1 and 2.

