### **8.2.2 Assessment of COVID-19 Signs, Symptoms, and Functional Status**

The investigator or medically qualified designee (consistent with local requirements) will assess COVID-19 signs and symptoms daily while the participant is hospitalized. After participant discharge, signs and symptoms will only be assessed on study visit days. Functional status will only be assessed at Day 1, Day 3, EOT, Day 10, Day 15, and Day 29.

The participant's ability to independently perform daily activities with minimal or no symptoms will be assessed and evaluated at the discretion of the investigator/designee.

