**Secondary:**

- All-cause mortality through Day 29
- Odds of a more favorable response on Pulmonary score at Day 3, EOT, Day 10, Day 15, and Day 29
- Odds of a more favorable response on Pulmonary+ score at Day 3, EOT, Day 10, Day 15, and Day 29
- Odds of a more favorable response in the clinical risk of mortality category from the National Early Warning Score at EOT
- Odds of a more favorable response on the WHO 11-point ordinal scale on Day 3, EOT, Day 10, Day 15 and Day 29. This scale provides a measure of illness severity across a range from 0 (not infected) to 10 (dead).

Note: All ordinal scores will be determined programmatically by the Sponsor based on relevant data collected in eCRFs. Relevant data to support determination of each ordinal score will be collected in eCRFs as follows:

- Pulmonary and Pulmonary+ scores: supplemental oxygen use and methods, oxygen saturation, dialysis and vasopressor use, vital status, adverse events, and investigator assessment of the participant's ability to independently perform daily activities with minimal or no symptoms
- NEWS: vital signs (i.e., respiratory rate, pulse rate, blood pressure, temperature, oxygen saturation) and investigator assessment of the participant's level of consciousness using the Alert, Voice, Pain, Unresponsive scale
- WHO 11-point scale: central laboratory SARS-CoV-2 RNA results, supplemental oxygen use and methods, oxygen saturation, dialysis and vasopressor use, vital status and investigator assessment of the participant's ability to independently perform daily activities with minimal or no symptoms

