A sensitivity analyses for the primary efficacy endpoint will be performed in the MITT population that does not impute “failure to recover” for participants who initiate Sponsor-designed standard of care for treatment for COVID-19 following start of randomized study therapy. In the case where the number of participants who require re-hospitalization but are then discharged again (or medically ready for discharge) before Day 29 exceeds 5% of the total MITT population, an additional sensitivity analysis will be performed in which all participants with re-hospitalizations by Day 29 are considered as not meeting the primary endpoint.

If superiority of MK-4482 over placebo is demonstrated as assessed by time-to-sustained recovery at the end of Part 2, the superiority of MK-4482 over placebo as assessed for the key secondary endpoint of all-cause mortality at Day 29 will be tested. Due to the relatively low number of deaths expected and the large number of strata levels, the unstratified Miettinen and Nurminen method [Miettinen, O. 1985] will be used to estimate and test the treatment difference for all-cause mortality. Every effort will be made to ascertain survival status for all participants. Missing data for this endpoint will be treated as failure (M=F approach) in the MITT population.

Ordinal outcome scales such as Pulmonary and Pulmonary+ will be analyzed using the cumulative logits function and the proportional odds model as described by McCullagh [McCullagh, P. 1980]. This methodology provides an estimate of the common odds ratio for assessing differences between treatment groups. In addition to a term for treatment group, the model will include terms for the stratification factors specified in Section 6.3.2. In addition, the proportion of participants in each ordinal scale category by treatment groups will also be presented.

The National Early Warning Score and the WHO 11-point ordinal scale score will be categorized to ordinal outcomes and will be further analyzed using the same approach as for Pulmonary and Pulmonary+ outcomes.

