EOT=End of Treatment; MITT= modified intent-to-treat; M & N= Miettinen and Nurminen; PP=Per-protocol; WHO=World Health Organization.				

a P=Primary approach; S=Supportive approach.

b Statistical models are described in further detail below:

c The stratified log-rank test includes stratification factors specified in Section 6.3.2.

d Stratified Cox Proportional Hazards regression includes terms for treatment, stratification factors specified in Section 6.3.2.

e Unstratified Miettinen and Nurminen method.

f Proportional odds model includes terms for treatment and stratification factors specified in Section 6.3.2.

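### The ordinal-scale models omit the Day 1 score, which can be derived from data already collected; adding it would gain precision by an amount the documents do not fix

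*Combined protocol and SAP*

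**What the plan says.** Section 9.6.1 sets the terms of the proportional odds model for Pulmonary and Pulmonary+: "In addition to a term for treatment group, the model will include terms for the stratification factors specified in Section 6.3.2". The proportional-odds footnote to Table 5 agrees: "Proportional odds model includes terms for treatment and stratification factors specified in Section 6.3.2". NEWS and the WHO scale are grouped into ordinal outcomes and "further analyzed using the same approach as for Pulmonary and Pulmonary+ outcomes", so the specification covers all four scales.

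Section 6.3.2 lists three factors: time from symptom onset (up to 5 days or longer), age (up to 60 years or older) and remdesivir use by the time of randomization. Severity is not among them; the same section only limits severe participants to 50% of the planned sample.

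The components of a Day 1 score are collected:
- Section 8.2.2: "Functional status will only be assessed at Day 1, Day 3, EOT, Day 10, Day 15, and Day 29".
- Section 1.3, footnote b: vital signs, signs and symptoms, "respiratory measures, oxygen therapy, ongoing medical history) must be completed and documented on Day 1 prior to calling IRT in order to randomize". Everything else scheduled for that day has to precede the first dose.
- The Schedule of Activities also places level of consciousness (needed for NEWS) and swabs (needed for WHO) on Day 1.
- Section 9.4.1.1: "All ordinal scores will be determined programmatically by the Sponsor based on relevant data collected in eCRFs".

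**The concern.** Participants enter at quite different points on these scales. Under Appendix 9 they range from mild disease with no added oxygen for COVID-19 to severe disease on more than 2 L/min. Where a participant starts is likely to predict where that participant stands a few days later, yet no measure of starting severity is in the model or in the stratification. An outcome model that leaves out a prognostic baseline value has less power than one that includes it. It also leaves any chance difference between arms in starting oxygen need inside the treatment estimate.

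At stake is the precision of 16 secondary comparisons: three scales at five visits, plus NEWS at EOT. Section 9.1 lists them as key secondary endpoints. Part 1 efficacy is analysed separately at about 75 per arm, and Section 9.7 has key efficacy results considered in dose selection.

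**Working it through.** **Is there a planned figure to reproduce?** Not for these scales. Section 9.9.1 gives 90% power for time to sustained recovery only. That figure reproduces. With 685 events and a rate ratio of 1.3, (√685/2) × ln 1.3 = 13.09 × 0.262 = 3.43, and Φ(3.43 − 1.96) gives 93.0% for a single look at one-sided 0.025. With the two-stage gamma (−1) design and the 1.071 futility bound obeyed, power is 90.4%. It has no bearing on the ordinal models.

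**Inputs from the documents.** About 1000 participants, 1:1 (Section 4.1, Part 2). One-sided 2.5% is borrowed from the primary analysis. Everyone is hospitalized on Day 1 (Section 8.11.2.2) and critical disease is excluded (Section 5.2), so Day 1 Pulmonary is mostly 1 to 4 and Day 1 WHO is almost only 4 or 5.

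**Assumed inputs.** Conditional treatment odds ratio (OR) 1.3 or 1.4; three outcome distributions resembling Day 3/EOT, Day 10/15 and Day 29; three Day 1 distributions; an OR of 1.5 to 5 per Day 1 category for the link between baseline and outcome.

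**Calculation 1: expected-data likelihood ratio.** The model is logit P(Y ≤ k) = α_k + treatment + stratification [+ Day 1 category], with one two-level stratification factor (log OR 0.7) in both versions. Power = Φ(√LR − 1.96), where LR is the likelihood-ratio statistic on the expected data. The equivalent sample-size ratio is [(1.96 + z_with)/(1.96 + z_without)]², where z is the normal quantile of the power. For treatment OR 1.4, four Day 1 Pulmonary levels and a Day 3/EOT-like outcome:

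| OR per Day 1 level | Rank correlation | Power without | Power with | Gain (points) | N ratio |
|---|---|---|---|---|---|
| 1.5 | 0.18 | 82.6% | 84.2% | 1.5 | 1.04 |
| 2 | 0.31 | 79.5% | 83.9% | 4.4 | 1.12 |
| 3 | 0.45 | 72.8% | 83.5% | 10.7 | 1.31 |
| 5 | 0.59 | 61.8% | 82.5% | 20.7 | 1.64 |

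Gains were taken before rounding. Check of the third row: z = 0.607 and 0.974, so (2.934/2.567)² = 1.31.

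With a Day 29-like outcome and the same step ORs, the gains are 1.2, 3.5, 8.1 and 15.1 points. For WHO with Day 1 limited to 4 or 5, they run from 0.4 to 7.7 points over all scenarios.

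**Calculation 2: all three planned factors in both models.** Simulation with 500 per arm, OR 1.4, Day 1 Pulmonary categories 1–4 at 5/35/35/25%, and 250 trials per setting. Remdesivir use was assumed at 5/15/55/75% across those categories, and age modestly related to Day 1 status and outcome.

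| Rank correlation | Planned terms | Plus Day 1 score | Gain (points) | Added information |
|---|---|---|---|---|
| 0.36 | 77% | 81% | 4 | 11% |
| 0.49 | 72% | 78% | 6 | 21% |
| 0.61 | 63% | 74% | 11 | 44% |

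Each power has a Monte Carlo standard error of about 3 points (√(0.72 × 0.28/250) = 0.028), so these are approximate.

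**Chance imbalance.** If half of participants are severe (the cap), the 95% range for the difference between arms in percent severe is ±1.96 × √(2 × 0.5 × 0.5/n). That is ±6 points at n = 500 and ±16 points at n = 75.

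**Validity.** In a separate simulation without stratification factors (400 trials per setting), null rejection rates were 0.0125–0.0375 without the Day 1 score and 0.015–0.025 with it, against a nominal 0.025 and Monte Carlo error of about 0.008. Neither model shows inflation.

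**The case against.** A reader might infer that all four scales lose substantial power. The documents do not support that. There is no planned ordinal power to fall short of, and gains of about 10 points or more on the Pulmonary scale need a strong baseline link: rank correlation of about 0.4 or more in calculation 1, and 0.61 in calculation 2. A comparator without the planned covariates also overstates the gain. Leaving out all three gave gains of 6, 13 and 26 points at correlations 0.36, 0.49 and 0.61; with them, under the assumptions above, the gains were 4, 6 and 11. Remdesivir use in particular may partly stand in for oxygen need. Day 1 WHO is little more than an oxygen yes/no flag, and NEWS was not modelled because Appendix 8 gives no risk-category cut-offs.

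A reader might also infer that the planned odds ratio is biased toward 1. It is not. Odds ratios are non-collapsible: in the third row of the first table the model without the Day 1 score estimates 1.34 where the conditional value is 1.40, and these are different quantities. Chance imbalance is likewise already reflected in the standard error.

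The ordinal scales lie outside the alpha-controlled sequence in Section 9.8, and category proportions by arm will be shown as well. Sparse Day 1 levels are a real difficulty: a 5% category holds about 4 of 75 participants per arm in Part 1. These points lower the consequence and shape the remedy. They give no reason to leave the Day 1 score out, since every calculation showed a gain from adding it.

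**Conclusion.** The concern holds as a matter of efficiency. All four models adjust only for the Section 6.3.2 factors and omit a prognostic baseline value that the trial can derive. Under assumed inputs the gain from including it is about 1 to 20 power points on a Pulmonary-type scale, roughly 4 to 11 points in the run with all three planned factors in both models, and at most about 8 points for WHO. It is likely largest at Day 3 and EOT, on the assumption that Day 1 status predicts best at early visits. No figure is available for NEWS. The range rests on a baseline-outcome association that the documents do not give. The planned analysis remains a valid, unbiased randomized comparison of a less conditional odds ratio.

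**What to change.** Before unblinding, amend Section 9.6.1 and the proportional-odds footnote of Table 5, or record the change in the supplemental SAP as Section 9 allows for non-confirmatory analyses. Each proportional odds model should include the Day 1 (pre-dose) score on the same scale as a prespecified covariate, alongside the stratification factors. For NEWS, use the Day 1 risk category with the same cut-offs as the EOT outcome.

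State two rules with it: how sparse Day 1 levels are pooled, which matters most in Part 1 at about 75 per arm, and how a missing Day 1 score is handled.

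The cost is one derived variable per scale, with no new data collection. The odds ratio becomes conditional on the Day 1 score, and the tables must label it so.

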Time-to-sustained recovery from randomization through Day 29	P (MITT) S (PP)	Stratified log-rank test c  Stratified Cox Proportional Hazards regression d	MITT PP	
Missing data will not be imputed.
 
Participants who initiate Sponsor-designated standard of care for treatment for COVID-19 48 hours or more following start of randomized study therapy will be treated as a failure to recover.
 
A sensitivity analysis for the primary efficacy endpoint will be performed in the MITT population that does not impute “failure to recover” for participants who initiate Sponsor-designated standard of care for treatment for COVID-19.
 
Depending upon the number of participants who required re-hospitalization but were discharged or medically ready for discharge again before Day 29, an additional sensitivity analyses will be performed in which all participants with re-hospitalizations by Day 29 are considered as not meeting the primary endpoint.
 
Failure to recover will be censored at Day 29. Death will also be censored at Day 29. Recovery followed by subsequent lost to follow up before Day 29 will be censored at the day of lost to follow up. Withdrawal (ie, discontinuation from the study for reasons other than death or lost to follow up) before Day 29 will be censored at the day of discontinuation.

Endpoint/Variable (Description, Time Point)	Primary vs. Supportive Approach a	Statistical Method b	Analysis Population	Missing Data and Data Imputation Approach
Secondary Endpoints				
All-cause mortality through Day 29	P (MITT) S (PP)	Unstratified M & N method c	MITT PP	Missing = Failure (M=F) – MITT Data as Observed (DAO) - PP
Odds of a more favorable response on Pulmonary score at Day 3, EOT, Day 10, Day 15, and Day 29	P (MITT) S (PP)	Proportional odds model d	MITT PP	Model-based
Odds of a more favorable response on Pulmonary+ score at Day 3, EOT, Day 10, Day 15, and Day 29	P (MITT) S (PP)	Proportional odds model d	MITT PP	Model-based
Odds of a more favorable response in the clinical risk of mortality category from the National Early Warning Score at EOT	P (MITT) S (PP)	Proportional odds model d	MITT PP	Model-based
Odds of a more favorable response on the WHO 11-point ordinal scale on Day 3, EOT, Day 10, Day 15 and Day 29	P (MITT) S (PP)	Proportional odds model d	MITT PP	Model-based

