### 10.8.2 National Early Warning Score

The National Early Warning Score is as follows [Royal College of Physicians 2012]:

Physiological Parameter	Point Value
Respiration Rate (breaths per minute)	
$\leq 8$	3
9-11	1
12-20	0
21-24	2
$\geq 25$	3
Oxygen Saturation (%)	
$\leq 91$	3
92-93	2
94-95	1
$\geq 96$	0
Any Supplemental Oxygen	
Yes	2
No	0
Temperature (°C)	
$\leq 35.0$	3
35.1-36.0	1
36.1-38.0	0
38.1-39.0	1
$\geq 39.1$	2
Systolic BP (mmHg)	
$\leq 90$	3
91-100	2
101-110	1
111-219	0
$\geq 220$	3
Heart Rate (beats per minute)	
$\leq 40$	3
41-50	1
51-90	0
91-110	1
111-130	2
$\geq 131$	3
Level of Consciousness	
A	0
V,P,U	3

A, V, P, U= Alert, Voice, Pain, Unresponsive

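### The plan gives no rule for death in the NEWS analysis at EOT; as written, participants who die without an EOT assessment would be left out

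*Combined protocol and SAP*

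**What the plan says.** NEWS is a secondary endpoint, analyzed at one post-baseline visit. Table 5 lists it as "Odds of a more favorable response in the clinical risk of mortality category from the National Early Warning Score at EOT". Section 9.6.1 states that "The National Early Warning Score and the WHO 11-point ordinal scale score will be categorized to ordinal outcomes" and that these "will be further analyzed using the same approach as for Pulmonary and Pulmonary+ outcomes", which means a proportional odds model with treatment and the stratification factors. The missing-data entry for NEWS in Table 5 says only that handling is model-based. The rule that counts missing data as failure is given for all-cause mortality alone.

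Section 9.4.1.1 lists the data from which each ordinal score is derived:

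- Pulmonary and Pulmonary+: the list includes "dialysis and vasopressor use, vital status, adverse events, and investigator assessment".
- WHO scale: the list includes "dialysis and vasopressor use, vital status and investigator assessment of the participant's ability".
- NEWS: "NEWS: vital signs (i.e., respiratory rate, pulse rate, blood pressure, temperature, oxygen saturation) and investigator assessment of the participant's level of consciousness", using the AVPU scale. Vital status does not appear, and neither does supplemental oxygen use.

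Appendix 8 makes death category 7 on Pulmonary and Pulmonary+ and score 10 on the WHO scale. The table in Section 10.8.2, introduced by "The National Early Warning Score is as follows", has seven physiological parameters with point values. It has no death level, and no thresholds that turn points into risk categories.

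**The concern.** The endpoint is meant to describe risk of mortality, yet the plan has nowhere to put a participant who has died. If such participants leave the analysis, the arms are compared among those who survived to be assessed, and that group is formed after randomization. If one arm has fewer early deaths, it keeps participants whom the other arm loses, and those kept are likely to be among the sickest. The other arm's worst outcomes are not counted. The comparison is then tilted against the arm that prevents deaths.

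The sponsor accepts this principle elsewhere. In the primary analysis, Section 9.6.1 carries deaths to Day 29 so that censoring at the time of death does not introduce bias. No corresponding step is given for NEWS.

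**Working it through.** **Does the text lead to omission?**

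1. A death cannot be scored from the stated NEWS inputs, because vital status is not among them and the scale has no death level.
2. The Schedule of Activities has level of consciousness assessed only on Day 1 and at EOT. NEWS therefore has one scheduled post-baseline value, and no series of scores from which a longitudinal model could borrow.
3. A proportional odds model for one visit has no likelihood term for a participant without an outcome. Under model-based handling that participant is omitted.
4. Section 9.6 says it covers the methods for secondary objectives and defers only other exploratory methods to the sSAP. The rule is not assigned elsewhere.

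**How large is the effect?** The documents give no NEWS distribution, no early-death rate and no power for this endpoint, so there is no stated figure to reproduce. What follows is an illustration.

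Inputs:
- 500 per arm, from Section 9.9.1.
- Three risk categories, from best to worst, in proportions 65/20/15% (assumed).
- Early deaths, MK-4482 versus placebo: 5 versus 15, or 2 versus 5 (assumed).

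Model: logit P(category j or better) = c_j + b × treatment. The common odds ratio (OR) is exp(b), fitted by maximum likelihood to expected counts without stratification factors. Above 1 favors MK-4482. It is fitted with death as a fourth, worst category, and again with deaths removed.

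*Scenario A: survivors split alike in both arms.* With 5 versus 15 deaths, survivors number 495 and 485. Best-category counts are 0.65 × 495 = 321.75 and 0.65 × 485 = 315.25.
- Deaths included, best category versus the rest: (321.75/178.25) / (315.25/184.75) = 1.06.
- Deaths included, best two versus the rest: (420.75/79.25) / (412.25/87.75) = 1.13. The common OR is 1.09.
- Deaths dropped: the distributions are identical and the OR is 1.00.

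*Scenario B: each averted death becomes a highest-risk survivor.* Worst category plus death is fixed at 75 per arm, giving 325/100/70 plus 5 deaths versus 325/100/60 plus 15 deaths.
- Deaths included: the first two cut-points give exactly 1.00 and only the death cut-point differs. The common OR is 1.01.
- Deaths dropped: (325/170) / (325/160) = 0.94 and (425/70) / (425/60) = 0.86. The common OR is 0.93.

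| Early deaths (MK-4482 vs placebo) | Scenario | OR, death worst | OR, deaths dropped |
|---|---|---|---|
| 5 vs 15 | A | 1.09 | 1.00 |
| 5 vs 15 | B | 1.01 | 0.93 |
| 2 vs 5 | A | 1.02 | 1.00 |
| 2 vs 5 | B | 1.00 | 0.98 |

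A different survivor split changes little: with 60/25/15% in Scenario A, 5 versus 15 deaths give 1.08 and 1.00.

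**Against sampling error.** The standard error of the log OR is about 0.13. For 5 versus 15 deaths the shift is ln(1.09/1.00) = 0.086 in A and ln(1.01/0.93) = 0.082 in B, each about 0.6 to 0.7 of a standard error. For 2 versus 5 deaths it is about 0.02, or 0.15 of a standard error.

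**The case against.** **The plan never says that deaths are dropped.** This is correct. The NEWS categories are undefined, and a worst level for death could still be added before unblinding. Omission is what the stated inputs and model produce; it is not a declared rule. The promise to analyze NEWS as the Pulmonary scales are analyzed does not settle the matter, because those scales handle death through their own categories and inputs.

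**Not every death before Day 5 to 7 would be lost.** This also stands. EOT is the day of the last dose, and Section 8.11.3 asks participants who stop treatment early to complete EOT activities then. Someone who stops on Day 3 and dies on Day 5 can have a score. The omission concerns deaths without an EOT assessment. For a participant assessed early who then dies, the plan does not say whether the score or the death counts.

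**Early deaths should be few.** Section 5.2 excludes critical COVID-19 and participants not expected to survive 48 hours, and Section 9.6.1 expects relatively few deaths even through Day 29. The illustrated death counts are assumptions, and 5 versus 15 is a large imbalance for so short a period.

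**Deaths still count elsewhere.** Pulmonary, Pulmonary+ and the WHO scale score death at the same visit, and mortality is hypothesis H2. Section 4.2.1.1.3 calls NEWS supportive, and Section 9.8 tests only H1 and H2. This limits the consequence but leaves the NEWS estimate as it is.

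**Conclusion.** The gap is real and minor. As written, the NEWS comparison would condition on survival to an EOT assessment, to the disadvantage of the arm with fewer early deaths. Under the assumptions shown, the common odds ratio moves by 0.02 to 0.09, less than one standard error. The primary conclusion and the alpha-controlled tests are unaffected.

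Two stronger readings are tempting and are not supported:

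- A reader might infer that dropping deaths reverses the direction of the NEWS result. The pair 1.01 and 0.93 arises only in Scenario B, where fixing worst-or-dead at 15% in both arms forces the result with death included to be nearly null. The 95% intervals are 0.79 to 1.31 and 0.71 to 1.20. When survivors split alike, the effect is attenuated from 1.09 to 1.00, with no reversal.
- A reader might extend the point to the WHO scale, which the same sentence of Section 9.6.1 names. That scale scores death as 10 and lists vital status, so it is not affected.

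**What to change.** In Section 9.6.1 and Table 5, define the NEWS risk categories with their score thresholds. State that death on or before the participant's scheduled EOT goes into an added category, worse than the highest-risk one, in the proportional odds model. Say that this applies even when an earlier EOT assessment exists after early discontinuation.

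In Section 9.4.1.1, add vital status to the NEWS inputs. Add supplemental oxygen use as well: Section 10.8.2 scores it at 2 points, but the input list omits it. That is a separate listing omission, best corrected in the same edit.

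The cost is a few sentences and a small change to the derivation program. No new data are needed, since deaths and oxygen use are already recorded under Sections 8.2.6 and 8.2.4. The rule should be fixed before unblinding, because a death rule chosen afterwards is open to challenge. Section 9 allows changes to non-confirmatory analyses to be documented in the sSAP.
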